Appendix 2 Fime and Events Table

1. Vital signs will be measured before dosing and every 4 hours after first dose. Blood pressure (BP) and heart rate (HR) for visit 2-4 will be measured in both the supine and standing positions in each time-points

- 2. Serum pregnancy test will be done at screening visit
- 3. Urine pregnancy test will be done at day -1 for each admission visit and biweekly during follow up visit
- 4. ECG (x3) will be performed according to table 2
- 5. Clinical lab assessment will be performed at screening visit (visit 1), day -1 and day 3 of each admission visit (visit 2-4) and weekly during follow up visit (see appendix 4 for the detail)
- 6. PK sample will be collected according to table 2 and appendix 4
- 7. Study drug administration will be administered according to table 1 and 2 and appendix 3
- Genetic sample can be collected at any of the subsequent visit if the blood draw at the visit 2 is missed
 Adverse events will be monitored until the last follow up visit.
- 10. Concomitant medications will be monitored until last follow up visit.
- 11. If interval between screening (visit 1) and on day -1 visit 2 is three days or less, the clinical laboratory screening test result and serum pregnancy test result can be used for enrolment evaluation on day -1 visit 2. In such cases, these tests would not need to be repeated at day-1 visit 2.
- 12. Holter monitoring will be performed on day -1, admission visit, D7 and D28 of visit 2, visit 3, and visit 4

Appendix 3

Drug dosing schedule

Artemether-lumefantrine dosing schedule								
One tablet A/L contains 20 mg artemether and 120 mg lumefantrine.								
	No. of tablets recommended at approximate timing of dosing							
Weight:	:: 0 h 8 h 24 h 36 h 48 h 60 h							
≥35 Kg	4	4	4	4	4	4		

Amodiaquine dispersible tablets dosing schedule						
One tablet contains 76.5 mg Amodiaquine.						
	No. of tablets recommended at approximate timing of dosing					
Weight:	0h	8h	24h	36h	48h	60h
35-41 Kg	2	2	2	2	2	2
42-55 Kg	3	3	3	3	3	3
≥ 56 Kg	4	4	4	4	4	4

Appendix 4

Total Blood Collection

visit		laboratory assessments	PK Sampling	Blood sampling	
Visit 1	Screening visit Clinical lab (Chemistry and Serum pregnancy test, HIV, Hep B, Hep C and TSH 6 mL, Hematology 2 mL, FBS 2 mL) (Total 10 mL)	10 mL	0	10 mL	
Visit 2	Day-1 (admission) Clinical lab (Chemistry 5 mL, Hematology 2 mL, and FBS 2 mL) (Total 9 mL)	9 mL	0	85 mL (Artemether - lumefantrine only)	
	Day 0-3 (admission) Clinical lab (Chemistry 5 mL, Hematology 2 mL, and FBS 2 mL) (Total 9 mL) Pharmacokinetic samples at Day 0 : Hr. 0 (pre-dose), 0.25, 0.5, 1, 2, 3, 4, 6, 8 (pre-dose), 10, 12, 14 Day 1 : Hr. 24 (pre-dose), 26, 28, 30, 36 (pre-dose), 38, 40, 42 Day 2 : Hr. 48 (pre-dose), 48.25, 48.5, 49, 50, 51, 52, 54, 56, 60 (pre- dose), 61, 62, 64, 66 Day 3 : Hr. 72 total 35 time-points (1 mL each time- points)	9 mL	35 mL	Or 100 mL (for amodiaquine only)	
	Day 4 (+1) (follow up) Pharmacokinetic samples (1mL)	0	1 mL		
	Day 7 (+/-2d) (follow up) Clinical lab (Chemistry 5 mL and Hematology 2 mL) (Total 7 mL) Pharmacokinetic sample collection (1mL)	7 mL	1 mL		
	Day 14 (+/-2d) (follow up) Clinical lab (Chemistry 5 mL and Hematology 2 mL) (Total 7 mL) Pharmacokinetic sample collection	7 mL	1 mL		

visit		laboratory assessments	PK Sampling	Blood sampling	
	(1mL)				
	Day 21 (+/-2d) (follow up)	7 mL	0		
	Clinical lab (Chemistry 5 mL and Hematology 2 mL) (Total 7 mL)				
	Day 28 (+/-2d) (follow up)	7 mL	1 mL		
	Clinical lab (Chemistry 5 mL and Hematology 2 mL) (Total 7 mL)				
	Pharmacokinetic sample collection (1 mL)				
	Day 35 (+/-2d) (follow up) (for Amodiaquine only)	7 mL	0		
	Clinical lab (Chemistry 5 mL and Hematology 2 mL) (Total 7 mL)				
	Day 42 (+/-2d) (follow up) (for Amodiaquine only)	7 mL	1 mL		
	Clinical lab (Chemistry 5 mL and Hematology 2 mL) (Total 7 mL)				
	Pharmacokinetic sample collection (1 mL)				
Visit	Day-1 (admission)	9 mL	0	85 mL	
3	Clinical lab (Chemistry 5 mL, Hematology 2 mL, and FBS 2 mL) (Total 9 mL)			(Artemether - lumefantrine only)	
	Day 0-3 (admission)	9 mL	35 mL	Or	
	Clinical lab (Chemistry 5 mL, Hematology 2 mL, and FBS 2mL) (Total 9 mL)			100 mL (for amodiaquine only)	
	Pharmacokinetic sample collection at				
	Day 0 : Hr. 0 (pre-dose), 0.25, 0.5, 1, 2, 3, 4, 6, 8 (pre-dose), 10, 12, 14				
	Day 1 : Hr. 24 (pre-dose), 26, 28, 30, 36 (pre-dose), 38, 40, 42				
	Day 2 : Hr. 48 (pre-dose), 48.25, 48.5, 49, 50, 51, 52, 54, 56, 60 (pre-dose), 61, 62, 64, 66				
	Day 3 : Hr. 72				
	Total 35 time-points (1 mL each time- points)				

visit		laboratory assessments	PK Sampling	Blood sampling
	Day 4 (+1) (follow up) Pharmacokinetic sample collection (1 mL)	0	1 mL	
	Day 7 (+/-2d) (follow up) Clinical lab (Chemistry 5 mL and Hematology 2 mL) (Total 7 mL) Pharmacokinetic sample collection (1 mL)	7 mL	1 mL	
	Day 14 (+/-2d) (follow up) Clinical lab (Chemistry 5 mL and Hematology 2 mL) (Total 7 mL) Pharmacokinetic sample collection (1 mL)	7 mL	1 mL	
	Day 21 (+/-2d) (follow up) Clinical lab (Chemistry 5 mL and Hematology 2 mL) (Total 7 mL)	7 mL	0	
	Day 28 (+/-2d) (follow up) Clinical lab (Chemistry 5 mL and Hematology 2 mL) (Total 7 mL) Pharmacokinetic sample collection (1mL)	7 mL	1 mL	
	Day 35 (+/-2d) (follow up) (for Amodiaquine only) Clinical lab (Chemistry 5 mL and Hematology 2 mL) (Total 7 mL)	7 mL	0	
	Day 42 (+/-2d) (follow up) (for Amodiaquine only) Clinical lab (Chemistry 5 mL and Hematology 2 mL) (Total 7 mL) Pharmacokinetic sample collection (1 mL)	7 mL	1 mL	
Visit 4	Day-1 (admission) Clinical lab (Chemistry 5 mL, Hematology 2 mL, and FBS 2 mL) (Total 9 mL)	9 mL	0 mL	140 mL
	Day 0-3 (admission) Clinical lab (Chemistry 5 mL,	9 mL	70 mL	

visit	laboratory assessments	PK Sampling	Blood sampling
Hematology 2mL ,and FBS 2mL) (Total 9 mL)			
Pharmacokinetic sample collection at			
Day 0 : Hr. 0 (pre-dose), 0.25, 0.5, 1, 2, 3, 4, 6, 8 (pre-dose), 10, 12, 14			
Day 1 : Hr. 24 (pre-dose), 26, 28, 30, 36 (pre-dose), 38, 40, 42			
Day 2 : Hr. 48 (pre-dose), 48.25, 48.5, 49, 50, 51, 52, 54, 56, 60 (pre-dose), 61, 62, 64, 66			
Day 3 : Hr. 72			
Total 35 time-points (2 mL each time- points) (1 mL for Artemether -lumefantrine and 1 mL for Amodiaquine			
Day 4 (+1) (follow up)	0	2 mL	
Pharmacokinetic sample collection (2 mL)			
Day 7 (+/-2d) (follow up)	7 mL	2 mL	
Clinical lab (Chemistry 5 mL and Hematology 2mL) (Total 7 mL)			
Pharmacokinetic sample collection (2 mL)			
Day 14 (+/-2d) (follow up)	7 mL	2 mL	
Clinical lab (Chemistry 5 mL and Hematology 2 mL) (Total 7 mL)			
Pharmacokinetic sample collection (2 mL)			
Day 21 (+/-2d) (follow up)	7 mL	0	
Clinical lab (Chemistry 5 mL and Hematology 2mL) (Total 7 mL)			
Day 28 (+/-2d) (follow up)	7 mL	2 mL	
Clinical lab (Chemistry 5 mL and Hematology 2mL) (Total 7 mL)			
Pharmacokinetic sample collection (2 ml)			
Day 35 (+/-2d) (follow up)	7 mL	0	

visit		laboratory assessments	PK Sampling	Blood sampling
	Hematology 2mL) (Total 7 mL)			
	Day 42 (+/-2d) (follow up)	7 mL	2 mL	
	Clinical lab (Chemistry 5 mL and Hematology 2 mL) (Total 7 mL)			
	Pharmacokinetic sample collection (2 mL)			
Genetic sampling (10 mL)		10 mL		10 mL
Genetic sample can be collected at any schedule visits.				
	345 mL

1. INTRODUCTION

Artemisinin combination therapies (ACTs) have been a major driving force behind substantial reductions in global malaria morbidity and mortality over recent years. However, further gains are threatened by the recent emergence of artemisinin resistance in Southeast Asia (1), a region that has been the epicentre for the evolution and spread of resistance to every important class of antimalarials.

There is an urgent need to evaluate alternative treatments where standard courses of ACTs are failing, and to develop combinations of drugs which will not fall rapidly to resistance and can be deployed immediately. As new drugs are at least five years away, we propose to combine artemisinin derivatives with two existing slowly-eliminated partner drugs; triple artemisinin combination therapy (TACT). The principle that multiple drugs with independent mechanisms of action prevent the emergence of drug resistance is proven in a range of human diseases. To assess the safety and tolerability and pharmacological interactions of the combination of artemether-lumefantrine and amodiaquine we propose an open label sequential trial of artemether-lumefantrine combined with amodiaquine. As we propose to combine artemether-lumefantrine, and amodiaquine, it is necessary that the potential interactions of these drugs be characterized.

2. STUDY OBJECTIVES AND ENDPOINTS

2.1 PRIMARY OBJECTIVE

- a. To characterize the potential pharmacokinetic interactions of artemether - lumefantrine and amodiaquine in healthy adult subjects.

2.2 PRIMARY ENDPOINT

Area under the concentration-time curve (AUC_{0-∞} and AUC_{0-last}) and maximum concentration (C_{max}) of artemether, lumefantrine and amodiaquine and their metabolites when given alone and in combination.

2.3 SECONDARY OBJECTIVES

- a. To characterize the pharmacokinetic properties of artemether-lumefantrine and amodiaquine when given alone and in combination.
- b. To evaluate the safety and tolerability of co-administered artemether-lumefantrine and amodiaquine. Protocol version 6.0 dated 22 June 2022 10 of 42.
- c. To investigate pharmacogenetic polymorphisms affecting drug levels of artemetherlumefantrine and amodiaquine and their metabolites.

STATISTICAL ANALYSIS PLAN FOR ALAQ STUDY

2.4 SECONDARY ENDPOINTS

- a. Elimination clearance (CL/F), terminal elimination half-life (t_{1/2}) and apparent volume of distribution (V_d) of artemether, lumefantrine and amodiaquine and their metabolites when given alone and in combination.
- b. Safety and tolerability parameters, including adverse events, electrocardiographic changes, vital signs and biochemical assessments. •
- c. Pharmacogenetic polymorphisms in the case of unusual metabolizeStudy design

2.5 GENERAL

This is an open-label pharmacokinetic study in 16 healthy Thai subjects. Subjects will be admitted in the inpatient ward and will be randomized to Artemether-lumefantrine followed by Amodiaquine or Amodiaquine followed Artemether-lumefantrine. There will be a washout period: > 6 weeks (after day 3) and then each of the participants will be given Artemether-lumefantrine + Amodiaquine. Thus, eEvery subject will have 1 screening and 3 admissions in the hospital.

All subjects will undergo screening assessments (visit 1). Screening assessments (visit 1) may be carried out over more than one day, provided that all required assessments are completed within the 14 days prior to visit 2. If the interval between screening (visit 1) and day -1 visit 2 is three days or less, the clinical laboratory screening test result and serum pregnancy test result can be used for enrolment evaluation on day -1 visit 2. In such cases, these tests would not need to be repeated at day1 visit 2

3. ANALYSIS**3.1 GENERAL CONSIDERATIONS**

The main strategy of analysis will be characterising the potential pharmacokinetic interactions of artemether - lumefantrine and amodiaquine . Safety analysis will also be done for potential signals and clinical importance. Means (SD) will be used to summarise normally distributed baseline variables. Non-normally distributed variables will be summarised using medians (IQR). Count data will be summarised using frequency counts and percentages. The percentages/proportions will be compared using Fisher's Exact test and a significance level of 5%. Detailed analysis approaches are provided in the relevant sections below.

STATISTICAL ANALYSIS PLAN FOR ALAQ STUDY

3.1.1 Data integrity

This study will be conducted in compliance with the protocol, relevant Standard Operating Procedures (SOPs), Good Clinical Practice (GCP) and the applicable regulatory requirement(s). All the analyses will be performed on clean data only.

3.1.2 Data cleaning and verification

All data will be cleaned and verified prior to statistical analysis. The data manager will ensure that clean data is submitted to the statistician who will coordinate with the pharmacologist for analysis. The statistician and the pharmacologist will cross-check that the available data for analysis is clean. Any data cleaning queries will need to be resolved before statistical and pharmacological analyses.

3.1.3 Locking the dataset

After data cleaning and responding to all data queries, the clean data will be locked normally in the database that was used for data capturing. The data may also be locked and stored in other user-friendly formats such as MS Excel and Stata. The locked data will be stored at an identifiable secure place and should be available to the relevant researchers upon request following proper request procedures. The data will also be in other backup media such as CDs or tapes.

3.1.4 Data format and Analysis logs

Data will be given to the Trial Statistician in compatible excel format (e.g. csv) who will coordinate with the Pharmacologist. The statistical analyses will be done in STATA (version 18) or R software while the pharmacokinetic analyses will be performed using PK specialised software such as Phoenix 64 or NONMEM as appropriate. Do files and scripts will be developed by the statistician and pharmacologist for the respective analysis components to be used to run the analyses. This will ensure reproducibility of the analyses. Logs (output from the script/do-files) and do files/ scripts will be kept by the statistician backed up on the server in a study folder for all analyses and made available upon request.

3.2 NUMBER OF PARTICIPANTS

This study will enroll 16 healthy subjects both male and female, aged 18-60 years, at the pharmacokinetic unit Faculty of Tropical Medicine, Mahidol University. Subjects will be healthy HIV-1, hepatitis B and C uninfected individuals who comprehend the purpose of the study and have provided written consent.

STATISTICAL ANALYSIS PLAN FOR ALAQ STUDY

[figure not shown]
3.3 STATISTICAL/ANALYTICAL ISSUES

3.3.1 Handling of dropouts or missing data

We expect most of the baseline variables to be collected as they form part of the inclusion/exclusion criteria. However, we expect to have some missing outcome data arising either from patients withdrawing from the study or being lost to follow-up. Available data analysis approach will be performed.

STATISTICAL ANALYSIS PLAN FOR ALAQ STUDY

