4. STUDY DESIGN

This is an open-label pharmacokinetic study in 16 healthy Thai subjects. Subjects will be admitted in the inpatient ward and will be randomized to **group A** or **group B** to receive 3 drug regimens described in the following table 1. Every subject will have 1 screening and 3 admissions in the hospital.

Visit 1	Screening					
	Within 14 days					
	Group A (n = 8)	Group B (n = 8)				
Visit 2	Regimen 1	Regimen 2				
	Artemether-lumefantrine	Amodiaquine				
	on Day 0, 1, and 2	on Day 0, 1 and 2				
	Washout period: > 6 we	eeks (after day 3)				
Visit 3	Regimen 2	Regimen 1				
	Amodiaquine	Artemether-lumefantrine				

 Table 1: Study Schedule

	on Day 0, 1 and 2	on Day 0, 1 and 2		
Washout period: > 6 weeks (after day 3)				
Visit 4	Regimen 3			
	Artemether-lumefantrine + Amodiaquine on Day 0, 1 and 2			

The total duration for each subject's participation in the study is approximately 6 - 8 months depend on washout period. Study duration is approximately 12 months.

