10.3 Subject discontinues the study drugs

Such subjects will be followed up for safety data collection. Reasons for this scenario may include:

- Pregnancy
- Subject requests to discontinue study drugs
- Abnormal renal and hepatic laboratory result including;
 - o Any creatinine above 1.5 x ULN OR increase 0.3 mg/dL above baseline
 - o Any ALT or AST above 3 x ULN
 - o Any elevation in total and direct bilirubin 2x ULN
 - o Any AST or ALT above 2xULN and TBL >1.5xULN

o Any AST or ALT above 2xULN with the appearance of fatigue, nausea, vomiting, right upper quadrant pain or tenderness, fever, rash and/or eosinophilia (eosinophil percent or count above the ULN)

If the abnormalities are potentially caused by one of the study drug the research physician will decide whether the other regimen of the study drugs should be continued. All laboratory abnormalities will be assessed by a trained physician. In case of abnormalities, a medical history to assess exposure to substances (medication, alcohol and others) with known toxicity for instance liver or kidney will be performed. In addition, the physician can perform additional investigations that are deemed necessary to explain the laboratory abnormalities (such as hepatitis serology or urine analysis). The liver function and creatinine abnormalities will be monitored until resolution or the stabilization of the condition. In any case all laboratory values should have returned to normal (within the normal range in the case of full blood count values and at least <1.5 times the ULN in case of the biochemistry values) before the administration of the next treatment round.

- QTc interval abnormalities;
- QTc or QT interval longer than 500 milliseconds

A case by case judgement will be made on whether the subjects should be discontinued from the study completely. All other drugs known to prolong the QTc interval will be stopped. QTc intervals will be monitored continuously until normalisation of the QTc interval to below 450 milliseconds. Magnesium and potassium levels will be measured and deficiencies will be supplemented through intravenous or oral medication.

Unevaluable subjects may be replaced, according to the discretion of the investigators with another subject of the same population, if either sample size or completeness of dataset is compromised. All data will be listed and will be valid for clinical safety and tolerability evaluation.

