10.4 Study Halting Rules

When three subjects experience adverse events of grade 3 or above that are "probably related or related" to the study drug, administration of study drug(s) will be halted and the investigator team will stop recruiting new study subjects promptly. Enrolled subjects who do not experience adverse event of grade 3 or above will receive study drug(s) until the study ends.

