12.5.2 Safety Analysis

Safety analyses will be based on the safety set. Safety and tolerability of artemether, lumefantrine and amodiaquine will be assessed by comparing the frequency (%) of adverse events and serious adverse events, with particular attention to abdominal pain, appetite perturbation and QT interval prolongation, using the Fisher's exact test. Safety data will be presented in tabular and/or graphical format and summarized descriptively. Any clinically relevant abnormalities or values of potential clinically concern will be described. Subjects will be analysed as treated.

An additional exploratory analysis evaluating independent renal markers against standard blood urea nitrogen/ creatinine levels will be conducted using appropriate statistical methods.

Adverse Events

All adverse event summaries will refer to treatment emergent adverse events, i.e. adverse

events that newly started or increased in intensity after the study drug administration. AE summaries will be generated for all AEs that occurred after study drug administration, until the end of the study.

12.6 Assessment of the relationship between pharmacokinetic parameters and ECG findings.

In addition to the results of the safety analysis, an exploratory analysis of the ECG data will be conducted. The ECG parameters will be compared with the PK properties of the drugs using appropriate statistical methods.

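### Safety of AL+AQ: the SAP has no adverse-event table by regimen, and an available-data comparison by regimen could understate harm because AL+AQ comes last and reaches only subjects who continued

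*SAP*

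**What the plan says.** **Order.** Protocol section 4 and Table 1 give AL and AQ alone in either order at Visits 2 and 3, 8 subjects per sequence, and AL+AQ at Visit 4. SAP 2.5 agrees: after washout, "then each of the participants will be given Artemether-lumefantrine + Amodiaquine".

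**Who reaches Visit 4.** Protocol 10.3 lists renal, hepatic and QTc criteria for stopping study drug. When a laboratory abnormality may be due to a study drug, "the research physician will decide whether the other regimen of the study drugs should be continued". Laboratory values must recover before the next round, and QTc cases are judged individually. After a halt under Protocol 10.4, "Enrolled subjects who do not experience adverse event of grade 3 or above will receive study drug(s) until the study ends". On replacement, 10.3 says "Unevaluable subjects may be replaced, according to the discretion of the investigators".

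**Safety comparison.** The safety set is everyone dosed (Protocol 12.2). Protocol 12.5.2 compares event frequencies by Fisher's exact test, names no comparison groups, and adds "Subjects will be analysed as treated". SAP 3.5.3 reports adverse events and serious adverse events by sequence group. It summarises laboratory results across treatment groups that it does not define, and it names no ECG table.

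**Missing outcomes.** SAP 3.3.1 expects withdrawals and loss to follow-up, and its whole rule is "Available data analysis approach will be performed". It gives no sensitivity analysis.

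**Objective.** Safety and tolerability of the co-administered drugs is a secondary objective (Protocol 2.2, SAP 2.3).

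**The concern.** Both sequence groups receive AL, AQ and AL+AQ, so a difference between them does not show whether the combination adds harm. An analyst who wants to answer the objective must build a table by regimen, as the as-treated wording suggests, and will fill it with available data.

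In that table a subject stopped for harm on a single drug counts under that drug and is absent under AL+AQ. Replacement does not restore the balance, because a replacement who reaches Visit 4 has passed the same selection. The events affected are those serious enough to stop dosing. At stake is an unsupported reassurance about a combination intended for patients.

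**Working it through.** **1. The plan's own figure.** The only relevant number is the sample size: "This is an open-label pharmacokinetic study in 16 healthy Thai subjects". Protocol 12.4 takes it from a cited minimum of 12 for bioequivalence. No stopping, dropout or event rate is given for this study, so there is nothing to reproduce. Every rate below is an assumption.

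**2. One selection step.** Let s be the share of susceptible people, p their event probability on the single drug, q their event probability on AL+AQ, and d the probability of not going on after an event.

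- Single-drug rate = s·p; true AL+AQ rate = s·q
- Available AL+AQ rate = q·s·(1 − p·d) / (1 − s·p·d)
- Bound over all dosed = s·p·d + q·s·(1 − p·d)

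First row: 0.8 × 0.25 × (1 − 0.4) / (1 − 0.1) = 0.12/0.90 = 13.3%; bound 0.10 + 0.12 = 22%.

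| Assumptions | Single | True AL+AQ | d | Available (ratio) | Bound (ratio) |
|---|---|---|---|---|---|
| s=0.25, p=q=0.8 | 20% | 20% | 0.5 | 13.3% (0.67) | 22% (1.10) |
| same | 20% | 20% | 1 | 5.0% (0.25) | 24% (1.20) |
| s=0.25, p=0.4, q=0.8 | 10% | 20% | 0.5 | 16.8% (1.68) | 21% (2.10) |
| same | 10% | 20% | 1 | 13.3% (1.33) | 22% (2.20) |
| s=1, p=q=0.2 (not person-specific) | 20% | 20% | 0.5 | 20% (1.00) | 28% (1.40) |
| same | 20% | 20% | 1 | 20% (1.00) | 36% (1.80) |

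With d = 0, available data give the true ratio q/p.

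**3. Two selection steps, as in the trial.** Give each subject a risk x from a beta distribution with mean p and within-subject correlation ICC, so a + b = 1/ICC − 1 and a = p(a + b). Take p = 20%, ICC = 0.3, d = 1 and no true difference: a = 0.467, a + b = 2.333.

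- First single regimen: 20.0%
- Second single regimen: a/(a+b+1) = 0.467/3.333 = 14.0%
- AL+AQ, available data: a/(a+b+2) = 0.467/4.333 = 10.8%, against a true 20%
- Pooled single regimens: (0.20 + 0.80 × 0.14)/1.80 = 17.3%
- Reaching Visit 4: 0.80 × 0.86 = 0.688, about 11 of 16
- Bound over all dosed: 0.312 + 0.688 × 0.108 = 38.6%

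For d below 1, the available AL+AQ rate is E[x(1−dx)²]/E[(1−dx)²], and the pooled single rate is (E[x] + E[x(1−dx)])/(1 + E[1−dx]). Over p 10–30%, ICC 0.1–0.5 and d 0.5–1, with no true difference, AL+AQ looks 0.7 to 13.8 points safer. With a true odds ratio of 2 (p = 20%, ICC 0.3), a true excess of 8.6 points appears as 4.0 (d = 0.5) or about zero (d = 1).

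Restricting to completers is no repair. With d = 1 they have no stopping event on a single drug by construction, so the comparison is 0% against 10.8%, a false excess for AL+AQ.

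**4. What the bound looks like at this size.** Suppose 3 events are seen on AL+AQ and k of 16 never reach it.

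| k | Observed | Possible range in all 16 |
|---|---|---|
| 1 | 3/15 = 20.0% | 3/16 to 4/16: 18.8–25.0% |
| 2 | 3/14 = 21.4% | 3/16 to 5/16: 18.8–31.3% |
| 4 | 3/12 = 25.0% | 3/16 to 7/16: 18.8–43.8% |

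If each subject has chance r of not reaching Visit 4, P(at least 2 lost) = 1 − (1−r)^16 − 16r(1−r)^15, which is 19%, 49% or 86% for r = 5%, 10% or 20%.

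**5. Why the bound needs all dosed subjects as denominator.** Suppose events come only from AL (s = 0.25, p = 0.8, d = 1, equal sequences; true AL+AQ rate 20%). If the denominator is AQ recipients only, subjects stopped after AL in the AL-first sequence vanish: (0.04 + 0.24)/(0.8 + 1) = 15.6%, below the truth. Over all dosed it is 0.20 + 0.04 = 24%.

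**The case against.** **The SAP contains no AL+AQ versus single-drug safety contrast to be biased.** This stands for adverse events: SAP 3.5.3 compares sequences, and the regimen contrast is only implied by the objective and by the as-treated wording. But then the SAP has no analysis that meets the objective, and any analysis that did would meet this selection.

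**The available-data rule is not the cause.** Largely right. A subject stopped under Protocol 10.3 is still followed for safety and has no AL+AQ outcome because AL+AQ was never given. Fixed order and conditional entry create the selection; the rule leaves it unaddressed.

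**The sizes are invented.** They are assumptions. Continuation is a case-by-case decision. Protocol 13.2 cites QTc prolongation in 7 of 20 malaria patients on amodiaquine, without saying that any reached the 500 ms criterion. Its amodiaquine hepatotoxicity figure, 1 in 15,600, concerns long-term use.

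**The bound counts events under a regimen never given, and overstates harm when events are not person-specific.** True: the ratio is 1.40 to 1.80 when the truth is 1.0. It belongs beside the available-data figure as a sensitivity result, not as an estimate or a decision rule.

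**Disclosure is partly planned.** Protocol 12.3 gives numbers dosed by drug group, and 10.2 records withdrawal reasons. Neither ties non-advancement to the regimen and the criterion met. The SAP's trial profile figure could not be seen.

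**Conclusion.** The point holds as a gap in the safety analysis. The SAP's adverse-event comparison by sequence cannot address co-administered safety. An available-data comparison by regimen can understate AL+AQ harm, provided that some subjects are stopped for harm on a single drug and that events tend to recur in the same people. If either condition fails, that bias is zero. The documents do not say how large it will be.

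A reader might infer that the planned analysis will make the combination look safer, with single-drug data from everyone set against AL+AQ data from the tolerant. The documents do not support that. The SAP does not plan that contrast, stopping is discretionary, and only the first period is unselected: the second single regimen also goes only to those who continued. Nor does either document plan a formal claim of no added harm.

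This is a low-cost improvement to a secondary objective.

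**What to change.** In SAP 3.3.1 and 3.5.3:

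1. Tabulate adverse events, laboratory events and QTc events by regimen and period, with the number entering each.
2. Add a row for subjects not advanced after AL and after AQ, with the criterion met. Show those who left for unrelated reasons separately.
3. Beside the available-data AL+AQ proportion, report a sensitivity bound over all dosed subjects. Count as an event everyone not advanced because of an adverse event, laboratory or QTc criterion after either single regimen. If others left for unrelated reasons, add the strict range that counts them both ways.
4. Call the regimen comparison descriptive, and do not state an absence of added harm from available data alone.

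Protocol 10.4 says both that administration is halted and that other enrolled subjects continue to receive drug. These statements must be reconciled, because they determine who reaches AL+AQ.

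Cost: SAP wording and a row and a column per table, from data already collected. The bound is conservative by design and can be wide with 16 subjects. If nobody is stopped for harm, it equals the available-data figure, apart from any unrelated losses.
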